#### Exclusion Criteria:

- 1. To increase the likelihood of a true diagnosis of COPD, we will exclude:
  - a) All patients less than 40 years of age on the index date, and
  - b) All patients with a diagnosis of asthma in the year prior to the index date
- 2. To limit the population to those without severe lung compromise outside of COPD, we will exclude individuals with lung cancer, interstitial lung disease, or lung transplant identified at any time prior to the index date
- 3. To restrict the cohort to new users of Tio+Olo or LABA/ICS, we will exclude any individual with use of either Tio+Olo, LABA/ICS, or LABA/LAMA/ICS

combination therapy in free or fixed form for at least one year prior to the index date.

Outpatient laboratory data is available for a subset of patients. Some analyses will be further restricted to the subset of the population with at least one laboratory result showing circulating eosinophil levels within six months before the index date.

Individuals in the study cohort will be followed from the index date until the earliest of the date of a switch in treatment, addition of either an ICS for the Tio+Olo group or of LAMA to the LABA/ICS group, discontinuation of COPD treatment, the end of the study period, or the end of continuous health plan eligibility. Main analyses will be further limited to the first year after cohort entry, with sensitivity analyses considering all available data.

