#### **8.4.2 Outcome(s)**

#### 8.4.2.1 Primary outcome(s)

The primary outcome event for effectiveness is time to first COPD exacerbation after cohort entry. The event is defined as follows:

• Severe exacerbation:

Proprietary confidential information © 2020 Boehringer Ingelheim International GmbH or one or more of its affiliated companies

- o Hospitalization with a principal discharge diagnosis of COPD.
- Moderate exacerbation:
  - o An ED visit with a discharge diagnosis of COPD, and/or
  - An antibiotic for a respiratory condition dispensed the same day as an oral corticosteroid

Time to the first COPD exacerbation will be measured from cohort entry until the occurrence of a hospitalization for COPD (severe exacerbation) or ED visit for COPD or prescription of an antibiotic and an oral corticosteroid on the same day (moderate exacerbation). Severe and moderate exacerbations will be considered as a composite for main analyses. Sensitivity analyses will stratify by exacerbation severity.

Although there is precedent for defining moderate exacerbation based on use of antibiotics for a respiratory infection without requiring concomitant oral corticosteroids, we have chosen a more restrictive definition of exacerbation. Because diagnoses listed on outpatient claims often correspond to a patient's past medical history in addition to acute problems, we expect limited ability to capture the indication for which antibiotics are prescribed. As such, including antibiotics alone as a case definition for exacerbation would introduce potentially substantial misclassification of outcome where antibiotics were truly given for non-respiratory infections. Given that our analyses will yield estimates on a ratio measure, non-differentially reduced sensitivity is a less important threat to validity than reduction of outcome specificity, which produces an expectation of bias towards the null hypothesis. In order to test our assumptions that the sensitivity of our outcome definition is not differential between the Tio+Olo and LABA/ICS groups, we would produce counts of patients with antibiotics alone during follow-up, and determine whether the proportion of potential exacerbations that we excluded through this design decision is comparable across groups.

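### The antibiotic-only count in Section 8.4.2.1 is too non-specific and too incomplete to support, by itself, the assumption that endpoint sensitivity is equal between arms

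*Combined protocol and SAP*

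**What the plan says.** The primary outcome in Section 8.4.2.1 has three routes: a hospitalization with COPD as principal diagnosis, an ED route ("An ED visit with a discharge diagnosis of COPD, and/or"), and a dispensing route ("An antibiotic for a respiratory condition dispensed the same day as an oral corticosteroid").

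The protocol declines to accept an antibiotic alone because the indication is poorly captured in claims: "including antibiotics alone as a case definition for exacerbation would introduce potentially substantial misclassification of outcome where antibiotics were truly given for non-respiratory infections". It argues that, for a ratio measure, lost sensitivity matters less than lost specificity provided the loss is non-differential. It then offers a check of that condition in these terms: "we would produce counts of patients with antibiotics alone during follow-up, and determine whether the proportion of potential exacerbations that we excluded". The share lost by declining antibiotics alone is to be set against the same share in the other arm.

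No decision threshold, weighting, person-time denominator or COPD-diagnosis requirement is stated for the check. The only sensitivity analysis that Section 8.4.2.1 names for this outcome is stratification by severity.

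**The concern.** The same-day rule discards three kinds of outpatient episode: antibiotic alone, oral steroid alone, and both drugs dispensed on different days. The check looks only at the first. That category was kept out of the endpoint because an unknown part of it is not exacerbation at all, so its size mixes missed exacerbations with other infections. Section 6 links long-term ICS use with pneumonia. Antibiotic use could therefore differ by arm for reasons unrelated to how well the endpoint captures exacerbations.

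The case for the restrictive definition rests on equal sensitivity. If sensitivity differs, the hazard ratio is shifted by roughly the ratio of the two sensitivities, and this check may not show it. The same applies in the eosinophil and exacerbation-history strata if treatment patterns differ there.

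**Working it through.** The plan attaches no figure to this check, so there is nothing to reproduce. The question is whether the check tracks what it is meant to test.

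**Definitions**
- Check = antibiotic-only episodes / (antibiotic-only + captured episodes). The protocol does not spell out the denominator; this is one natural reading of its proportion.
- Sensitivity = captured / true exacerbations.
- With good specificity, observed HR ≈ true HR × (sensitivity in Tio+Olo / sensitivity in LABA/ICS).

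**Inputs.** All are assumptions, because the documents give none. Each arm has 400 true exacerbations, of which 15% (60) are treated with an antibiotic alone. Other infections treated with an antibiotic alone are added to these.

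**(a) Equal check, unequal sensitivity**
- Arm A: captured 400 × 0.60 = 240; antibiotic-only 60 + 240 = 300; check 300/540 = 55.6%.
- Arm B: captured 400 × 0.50 = 200; antibiotic-only 60 + 190 = 250; check 250/450 = 55.6%.
- The check passes, while captured events stand in the ratio 200/240 = 0.83.

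**(b) Equal antibiotic-only count, unequal sensitivity.** The extra loss in arm B is all steroid-only or split-day, and each arm has 200 other infections.
- Both arms: antibiotic-only 60 + 200 = 260, so the raw counts are identical.
- Check: 260/500 = 52.0% against 260/460 = 56.5%, a gap of 4.5 points.
- With 100 other infections: 160/400 = 40.0% against 160/360 = 44.4%. With 400: 460/700 = 65.7% against 460/660 = 69.7%.

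**(c) Unequal check, equal sensitivity.** Sensitivity is 60% in both arms; other infections are 200 in one arm and 1.2 or 1.5 times that in the other.
- Reference arm: 260/500 = 52.0%.
- At 1.2 times (240): 300/540 = 55.6%, a gap of 3.6 points.
- At 1.5 times (300): 360/600 = 60.0%, a gap of 8.0 points.
- These false signals bracket the true signal of 4.5 points in (b), so the reading cannot tell the two situations apart.

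Under these inputs, true exacerbations make up between 60/460 = 13% and 60/160 = 38% of antibiotic-only episodes.

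**What a sensitivity gap would do to the HR (assumed values)**
- True HR 1.00: 0.60/0.55 gives 1.09; 0.60/0.66 gives 0.91. On the log scale these are 0.087 and 0.095.
- True HR 0.85: a sensitivity ratio of 0.50/0.60 = 0.83 gives 0.71; a ratio of 0.60/0.50 = 1.20 gives 1.02.
- For scale, |ln 0.85| = 0.163, where 0.85 is the hazard ratio that Section 8.7 quotes from a CPRD analysis. It is not a stated target of this study.

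These sensitivities refer to the whole composite. The same-day rule acts on one of three routes, so the gap in the dispensing route would have to be larger than the composite gap shown.

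**The case against.** Several points on the other side are sound.

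- **The check is not empty.** A reader might infer that it measures other infections instead of missed exacerbations. The documents do not support that: the protocol speaks of potentially substantial misclassification and gives no share. Flares treated with an antibiotic alone are also among those the same-day rule drops, so the check counts part of what is lost.
- **Follow-up length.** As-treated follow-up ends at, among other events, "addition of either an ICS for the Tio+Olo group or of LAMA to the LABA/ICS group, discontinuation of COPD treatment", so a reader might infer that unequal treatment duration distorts the check by itself. That applies to raw counts. The protocol goes on to compare a proportion, in which longer follow-up raises numerator and denominator together and largely cancels when events are uncommon. What remains is that the denominator is undefined.
- **Phenotype.** A reader might suppose that LABA/ICS starters are more eosinophilic and so more often given steroid alone. The preliminary counts in Section 8.7 do not point that way. Among patients with a result, those at or above 300 cells/µL are (481 + 105)/2,193 = 26.7% for Tio+Olo and (4,437 + 670)/19,278 = 26.5% for LABA/ICS. These counts are unadjusted and cover tested patients only. Asthma in the prior year is an exclusion, and the propensity score includes prior exacerbations and prior COPD treatments.
- **Other safeguards.** Severe events do not depend on the same-day rule. A severe-only HR that departs from the moderate one would be a warning, though not proof. Section 8.4.1 refers to Section 8.9.2 for sensitivity analyses, and that text is not available here, so an alternative outcome definition there cannot be ruled out. Quantitative bias analyses are planned, and outcome misclassification is acknowledged in Sections 8.6 and 8.11.
- **The remedy is also imperfect.** Steroid-only courses carry no captured indication either.

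These points limit the claim about size and mechanism. They do not turn an antibiotic-only comparison into a test of equal sensitivity.

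**Conclusion.** The concern holds in a limited form. The check in Section 8.4.2.1 is non-specific, because it counts a mixture, and incomplete, because it leaves out steroid-only and split-day episodes. As written it can pass when sensitivity differs and fail when it does not, so it cannot by itself support the assumption on which the restrictive definition depends.

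The size of any bias is unknown from the documents. The HR shifts in the working show scale under assumed sensitivities and do not predict a result. A reader might infer that the primary HR is biased, or biased in a particular direction. Nothing in the documents shows that sensitivity does differ between arms. The restrictive primary definition is reasoned and need not change. What needs repair is the evidence offered for its key assumption.

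**What to change.** In Section 8.4.2.1, replace the single count with a table by arm, propensity-weighted and per person-year of as-treated follow-up:

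- (a) oral-steroid courses without an antibiotic;
- (b) antibiotic and oral-steroid dispensings within a short pre-specified window (for example 7 days) but not on the same day;
- (c) antibiotic-only episodes, as a descriptive row.

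State that each row is an imperfect proxy for missed exacerbations.

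Add two separate sensitivity runs of the primary Cox model: one accepting both drugs within the window, and one also accepting steroid-only courses. Running them separately lets a shift in the HR be attributed to one change at a time. Read both beside the planned severity-stratified results. If Section 8.9.2 already contains such a definition, a cross-reference is enough for that part.

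Cost: protocol wording, one table and two model runs on data already extracted. The broader endpoints are less specific, so they remain sensitivity analyses and the primary endpoint is unchanged.

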#### 8.4.2.2 Secondary outcome(s)

The first secondary outcome is time to first hospitalization for community-acquired pneumonia (serious pneumonia). Pneumonia will be defined using ICD-9-CM diagnoses 481.x-486.x; 487.0, 507.x, 507.0, 507.1, 507.8, 510.0, 510.9, 511.0, 513.0, 514.x, 517.1, 519.8, 530.84, and ICD-10 diagnosis codes J10.0; J11.0; J12-J18; J22; J69; J85.0; J85.1; J86. This definition has been used successfully in COPD [P07-09514; P16-10095].

The second secondary outcome is time to a pharmacy dispensing indicating escalation to triple therapy, (i.e., addition of ICS to Tio+Olo or a LAMA to LABA/ICS).

The third secondary outcome is time to an adverse outcome including exacerbation, hospitalization for pneumonia, and escalation to triple therapy, defined as time from cohort entry until the earliest primary or secondary outcome as defined above (See Section 8.4.2.1, 8.4.2.2).

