#### 8.4 VARIABLES

#### 8.4.1 Exposures

The exposure measures are based on pharmacy dispensings of the two long-acting bronchodilators under study, namely fixed-dose combination of Tio+Olo and a fixed-dose combination of LABA and ICS, over one year of follow-up. As described in the data analysis section, the as-treated analysis, which is the main analysis, will consider exposure as current use of Tio+Olo or LABA/ICS within the treated groups defined as within the days supply recorded at the time of pharmacy dispensing, allowing for a gap between dispensings of up to 15 days. This gap is allowed in consideration of plausible delays in obtaining medication refills and continued use beyond the days supplied where medication has been missed due to imperfect adherence, and will be varied in sensitivity analyses (see Section 8.9.2). The treatment segment ends at the earliest of the following events:

- 1. Fifteen days after the end of the observed days supply for the medication received on the index date without a subsequent dispensing of COPD medication (i.e., discontinuation)
- 2. Initiation of triple therapy (i.e., addition of ICS to Tio+Olo or a LAMA to LABA/ICS (i.e., treatment escalation)
- 3. Any other change in use of study medication by active ingredient, inclusive of a change to a different combination therapy, change from a fixed form to a free form combination therapy, or a change from combination therapy to monotherapy (i.e., switch)

Changes in dose for medications started on the index date will not impact the end of the treatment segment. Codes used to identify study medications are included in Annex 3.1.

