#### 8.5 DATA SOURCES

This study will be conducted using the HIRD, a large administrative healthcare database maintained by HealthCore for use in health outcomes and pharmacoepidemiologic research. The HIRD includes longitudinal medical and pharmacy claims data from health plan

members across the United States (US). Member enrollment, medical care (professional and facility claims), outpatient prescription drug use, outpatient laboratory test result data, and health care utilization may be tracked for health plan members in the database dating back to January 2006, and with diagnoses recorded in International Classification of Disease, Version 10 (ICD-10) since October, 2015. Laboratory result data are additionally available for those tests that have been performed using two large, national reference laboratories (Quest and LabCorp) [R14-4278]. The database has been used for the study of numerous diseases, including studies of COPD [R19-2324; R19-2321; R19-2323; R19-2322; P15-11025; P14-12233].

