### **ANNEX 3.2: DEFINITIONS OF STUDY OUTCOMES**

See section 8.4.2. Complete list of codes will be added to this document after review and approval.

Condition	ICD9	ICD10	ICD9 proc	ICD10 proc	HCPCS	СРТ
COPD	491	J41				
	491	J41.0				
	491.1	J41.1				
	491.2	J41.8				
	491.21	J42				
	491.22	J43				
	491.8	J43.0				
	491.9	J43.1				
	492	J43.2				
	492	J43.8				
	492.8	J43.9				
	496	J44				
		J44.0				

Pneumonia	1		-		1
Pneumonia  480  J10.00  480.1  J10.01  J10.08  J11.00  J11.00			J44.1		
480.1 J10.01 480.2 J10.08 480.3 J11.00 480.8 J11.08 480.9 J12.0 481 J12.1 482 J12.2 482.1 J12.3 482.2 J12.81 482.3 J12.89 482.31 J12.9 482.32 J13 482.39 J14 482.4 J15.0 482.41 J15.1 482.42 J15.20 482.49 J15.211 482.81 J15.212 482.82 J15.29 482.83 J15.3 482.84 J15.4			J44.9		
480.2 J10.08 480.3 J11.00 480.8 J11.08 480.9 J12.0 481 J12.1 482 J12.2 482.1 J12.3 482.2 J12.81 482.3 J12.89 482.31 J12.9 482.32 J13 482.39 J14 482.4 J15.0 482.4 J15.0 482.41 J15.1 482.42 J15.20 482.49 J15.211 482.81 J15.212 482.83 J15.3 482.84 J15.3	Pneumonia	480	J10.00		
480.3 J11.00 480.8 J11.08 480.9 J12.0 481 J12.1 482 J12.2 482.1 J12.3 482.2 J12.81 482.3 J12.89 482.31 J12.9 482.32 J13 482.39 J14 482.4 J15.0 482.41 J15.1 482.42 J15.20 482.49 J15.211 482.81 J15.212 482.82 J15.29 482.83 J15.3 482.84 J15.4		480.1	J10.01		
480.8 480.9 J12.0 481 J12.1 482 J12.2 482.1 J12.3 482.2 J12.89 482.31 J12.9 482.32 J13 482.39 J14 482.4 J15.0 482.41 J15.1 482.42 J15.20 482.49 J15.211 482.81 J15.212 482.82 J15.29 482.83 J15.3 482.84 J15.4		480.2	J10.08		
480.9  481  J12.1  482  J12.2  482.1  J12.3  482.2  J12.81  482.3  J12.89  482.31  J12.9  482.32  J13  482.39  J14  482.4  J15.0  482.41  J15.1  482.42  J15.20  482.81  J15.212  482.82  J15.29  482.83  J15.3  482.84  J15.4		480.3	J11.00		
481 J12.1 482 J12.2 482.1 J12.3 482.2 J12.81 482.3 J12.89 482.31 J12.9 482.32 J13 482.39 J14 482.4 J15.0 482.41 J15.1 482.42 J15.20 482.49 J15.211 482.81 J15.212 482.82 J15.29 482.83 J15.3 482.84 J15.4		480.8	J11.08		
482 J12.2 482.1 J12.3 482.2 J12.81 482.3 J12.89 482.31 J12.9 482.32 J13 482.39 J14 482.4 J15.0 482.41 J15.1 482.42 J15.20 482.49 J15.211 482.81 J15.212 482.82 J15.29 482.83 J15.3 482.84 J15.4		480.9	J12.0		
482.1 J12.3 482.2 J12.81 482.3 J12.89 482.31 J12.9 482.32 J13 482.39 J14 482.4 J15.0 482.41 J15.1 482.42 J15.20 482.49 J15.211 482.81 J15.212 482.82 J15.29 482.83 J15.3 482.84 J15.4		481	J12.1		

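### Section 8.4.2.2 and Annex 3.2 print different pneumonia code lists, and the section pairs ICD-10 J12 with no ICD-9 480.x

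*Combined protocol and SAP*

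**What the plan says.** Section 8.4.2.2 makes hospitalization for community-acquired pneumonia the first secondary outcome. Its case definition is directive: "Pneumonia will be defined using ICD-9-CM diagnoses 481.x-486.x; 487.0, 507.x", then further ICD-9 codes (507.0, 507.1, 507.8, 510.0, 510.9, 511.0, 513.0, 514.x, 517.1, 519.8, 530.84), and "ICD-10 diagnosis codes J10.0; J11.0; J12-J18; J22; J69; J85.0; J85.1; J86". The section supports this with "This definition has been used successfully in COPD" and two citations. The third secondary outcome, the composite, takes its components from Sections 8.4.2.1 and 8.4.2.2.

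Annex 3.2, on outcome definitions, refers the reader back to Section 8.4.2 and adds "Complete list of codes will be added to this document after review and approval". It nevertheless prints a Pneumonia row of ICD-9 and ICD-10 codes. That row opens with the 480.x family and ends with 997.31 and 997.32 on the ICD-9 side and J95.4 and J95.89 on the ICD-10 side.

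The visible outcome text never sends the reader to Annex 3.2. The exposure text, by contrast, does name its annex: "Codes used to identify study medications are included in Annex 3.1".

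Section 8.5 dates ICD-10 recording in the database from October 2015. Section 8.3 accepts index dispensings from January 2013 to March 2019, so both coding systems supply events.

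**The concern.** There are two separate problems.

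First, the document prints two code lists for one outcome and does not say which prevails. A programmer who works from the annex, or merges the lists, obtains a different case definition from one who works from the section.

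Second, the section's own list looks uneven across the coding change. Its ICD-10 range begins at J12 and its ICD-9 range at 481. The annex places both 480.x and J12.x under Pneumonia, so the plan itself treats both families as pneumonia. Under the section's list, 480.x does not count before October 2015, while J12 counts afterwards.

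At stake are the first secondary outcome and the composite that contains it. Section 6 gives pneumonia under long-term ICS use as part of the study's rationale, so the outcome is not peripheral. If the arms were spread differently over calendar time, a definition that changes with the calendar could move the hazard ratio. The primary outcome does not use these codes.

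**Working it through.** **1. Annex against section.** Each entry in the annex's Pneumonia row was matched by prefix to the Section 8.4.2.2 codes and ranges.

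| | ICD-9 | ICD-10 | Total |
|---|---|---|---|
| Annex entries | 37 | 39 | 76 |
| Within the section list | 29 | 37 | 66 |
| Not in the section list | 8 | 2 | 10 |

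The ten are 480, 480.1, 480.2, 480.3, 480.8, 480.9, 997.31, 997.32, J95.4 and J95.89.

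**2. Section against annex.** Section codes with no entry in the annex row:
- ICD-9: 487.0, 507.x, 510.0, 510.9, 511.0, 513.0, 514.x, 517.1, 519.8 and 530.84 (ten, counting 507.x and its sub-codes once).
- ICD-10: J22, J85.0 and J86 (three). Of the J69 category, the annex has only J69.0.

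The annex's stated incompleteness may explain these gaps. It explains less readily why codes outside the section's list are already printed.

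**3. Across the coding change.** The section lists J12 but not 480.x. The annex lists six 480.x entries and seven J12.x entries (J12.0, J12.1, J12.2, J12.3, J12.81, J12.89, J12.9) under one heading. Its columns are parallel lists and not a crosswalk: the run "480.1 J10.01 480.2 J10.08 480.3 J11.00" sets 480.x beside J10.x and J11.x. So the annex shows that both families are regarded as pneumonia, but not that one maps to the other.

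**4. Calendar split.** January 2013 to September 2015 is 33 months and October 2015 to March 2019 is 42 months, so 33/75 = 0.44 of the calendar window is under ICD-9. This is not a share of patients, person-time or events.

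**5. Illustration by assumption.** The documents give no pneumonia counts by code, arm or year. Let v be the share of ICD-9-era pneumonia hospitalizations coded 480.x, the same in both arms. Let p0 and p1 be the shares of LABA/ICS and Tio+Olo follow-up in the ICD-9 era. With constant rates and no adjustment, leaving out 480.x multiplies the Tio+Olo versus LABA/ICS hazard ratio by about

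(1 − v·p1) / (1 − v·p0).

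With p0 assumed to be 0.44:

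| v | p1 = 0 | p1 = 0.22 | p1 = 0.44 |
|---|---|---|---|
| 0.01 | 1.004 | 1.002 | 1.000 |
| 0.05 | 1.022 | 1.011 | 1.000 |
| 0.10 | 1.046 | 1.023 | 1.000 |

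For example, with v = 0.10 and p1 = 0: 1/(1 − 0.044) = 1.046. This is not a bound, because p0 is borrowed from the calendar split. At the arithmetical limits for v = 0.10, the factor is 1/(1 − 0.10) = 1.111 (p0 = 1, p1 = 0) or (1 − 0.10)/1 = 0.900 (p0 = 0, p1 = 1). When both arms have the same era mix, it is 1.000.

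**The case against.** The best defence is that only one list operates. The section uses directive wording, the annex defers to it and awaits approval, and that approval could delete codes as well as add them. On that reading the ten annex-only codes never reach the analysis. This largely stands for the annex mismatch, except that no sentence sets an order of precedence. It does not answer the J12 without 480.x asymmetry, which lies within the section itself.

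A second defence is that the section adopts a published definition, so the omission of 480.x may be inherited. That cannot be checked from the documents. It is a reason to allow a sensitivity analysis in place of a change to the main definition.

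A third is that calendar year of cohort entry is a covariate and the propensity score is time-conditional (Section 8.4.4). Section 8.4.2.1, writing about exacerbations, also ranks non-differential loss of sensitivity as the lesser threat to a ratio measure. This stands as a reason to expect a small effect.

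Three stronger readings are tempting but unsupported:
- A reader might infer that viral pneumonia as a class counts only from October 2015. The plan prints no code labels, and the section's ICD-9 list contains other codes, 487.0 among them, that count before that date. Only the 480.x family is shown to be left out.
- A reader might infer that 997.31, 997.32, J95.4 and J95.89 contaminate the outcome with events that are not community-acquired. That depends on code meanings the plan does not print, and it matters only if the annex is programmed or merged in.
- A reader might infer that this is the only gap across the coding change. No full crosswalk of the section's list was made, so the number of gaps is unknown.

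**Conclusion.** The two printed lists differ, and the section's list, followed as written, changes the case definition for one code family part-way through the study. The code comparison is certain: 10 of 76 annex entries fall outside the section's list, and J12 is listed without 480.x. Here, outside means not listed; the section contains no explicit exclusion.

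That the section governs is the natural reading, not a stated rule. Pairing 480.x with J12 rests on the annex listing both under Pneumonia and should be confirmed against the code book.

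The effect on the hazard ratio cannot be computed from the documents and is probably small. The point ranks between minor and should-fix: it concerns the reproducibility of the first secondary outcome and the composite, and it gives no ground for doubting the primary analysis.

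**What to change.** - State that Section 8.4.2.2 governs, and make the Annex 3.2 Pneumonia row match it in both directions, including the section codes now missing from the annex.
- Add 480.x to the section's ICD-9 list to pair with J12. Alternatively, keep the cited definition as the main one and run the aligned list as a sensitivity analysis.
- Check 997.31, 997.32, J95.4 and J95.89 against the code book, and keep them out of the outcome list if they are not community-acquired events.
- Section 8.4.4 also uses pneumonia as a baseline comorbidity, and the visible Annex 3.3 has no pneumonia row. If the Annex 3.2 row serves that covariate too, give the covariate its own list, so that editing the outcome does not silently alter it.
- Report pneumonia event rates by arm before and after October 2015, unless Section 8.9.2 (cited in Section 8.4.1 but not visible in the public text) already provides for this.

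The cost is a code-list edit, one descriptive table and possibly one sensitivity run. Adding 480.x can only add qualifying hospitalizations, probably few, and departs slightly from the cited definition. The milestones put preliminary results at 19 December 2019, before the protocol date of 19 February 2020, so the change should record whether it was made with outcome counts already known.

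### The pneumonia outcome has two conflicting code lists and no stated diagnosis position, so non-pneumonia or hospital-onset stays can count as community-acquired pneumonia

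*Combined protocol and SAP*

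**What the plan says.** Section 8.4.2.2 names the first secondary outcome as "time to first hospitalization for community-acquired pneumonia (serious pneumonia"). The ICD-9 list opens with "Pneumonia will be defined using ICD-9-CM diagnoses 481.x-486.x; 487.0, 507.x" and continues through "510.0, 510.9, 511.0, 513.0, 514.x, 517.1, 519.8, 530.84". The ICD-10 list has J10.0 and J11.0 and then "J12-J18; J22; J69; J85.0; J85.1; J86". The justification offered is prior use: "This definition has been used successfully in COPD [P07-09514; P16-10095"]. The section gives neither a diagnosis position nor a rule that separates community from hospital onset.

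Section 8.4.2.1, by contrast, defines severe exacerbation as "Hospitalization with a principal discharge diagnosis of COPD".

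Annex 3.2, which covers outcome definitions, prints a second pneumonia list that differs from the first. Of the annex it says: "Complete list of codes will be added to this document after review and approval". Neither place says which list governs.

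The pneumonia event also enters the third secondary outcome, the composite of exacerbation, pneumonia hospitalisation and escalation to triple therapy.

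**The concern.** Two programmers working from this protocol could build two different pneumonia outcomes, and neither would match its name well. The body list admits codes that are not specific to pneumonia. The annex list admits codes that by label arise from ventilation or procedures. Without a position rule, a stay for another reason with such a code in a secondary field can also be counted.

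Section 8.4.2.1 argues, for exacerbations, that in a ratio analysis lost specificity matters more than lost sensitivity because it biases the estimate towards the null, and it chooses a restrictive definition for that reason. The pneumonia definition goes the other way without explanation. ICS-related pneumonia is part of the study's rationale (section 6), so a hazard ratio drawn towards 1 would understate the difference that this outcome is meant to detect.

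**Working it through.** The plan states no event count, validity figure or power for pneumonia, so there is no figure to reproduce. Three checks apply.

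**1. The two lists side by side** (section 8.4.2.2 against Annex 3.2)

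| | In 8.4.2.2 only | In Annex 3.2 only |
|---|---|---|
| ICD-9 | 487.0, 507.x, 510.0, 510.9, 511.0, 513.0, 514.x, 517.1, 519.8, 530.84 | 480 and 480.1 to 480.9, 997.31, 997.32 |
| ICD-10 | J22, J85.0, J86 (and J69 beyond J69.0) | J95.4, J95.89 |

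The conflict is visible from the codes alone. What the codes mean is not printed in the protocol, so the following rests on standard ICD labels:
- 511.0 is pleurisy, 514 includes pulmonary congestion, 519.8 is other diseases of the respiratory system, 530.84 is tracheoesophageal fistula, and J22 is unspecified acute lower respiratory infection.
- 997.31, 997.32 and J95.4 are ventilator-associated or procedure-related, and J95.89 is post-procedural.

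**2. Consistency across October 2015** (section 8.5 gives the date; the cohort runs from 2013 to 2019)

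- The body list has J12 but starts ICD-9 at 481, so it lacks 480.
- The annex has 480 and J12. It also has J10.0x, J11.0x and J69.0, but lacks 487.0 and 507.

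Under either list, the same illness can be an event in one coding period and not in the other.

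**3. Size of the dilution**

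Let f be the share of counted LABA/ICS events that are not community-acquired pneumonia, and suppose that those events occur at the same rate in both groups (HR 1). Then

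observed HR = (1 − f) × true HR + f.

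For a true HR of 0.70:
- f = 0.05: 0.95 × 0.70 + 0.05 = 0.715
- f = 0.10: 0.90 × 0.70 + 0.10 = 0.73
- f = 0.20: 0.80 × 0.70 + 0.20 = 0.76
- f = 0.30: 0.70 × 0.70 + 0.30 = 0.79

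The same formula for other true values:

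| True HR | f = 0.05 | f = 0.10 | f = 0.20 | f = 0.30 |
|---|---|---|---|---|
| 0.60 | 0.62 | 0.64 | 0.68 | 0.72 |
| 0.70 | 0.715 | 0.73 | 0.76 | 0.79 |
| 0.80 | 0.81 | 0.82 | 0.84 | 0.86 |

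Equivalently, 1 − observed HR = (1 − f) × (1 − true HR): the apparent effect shrinks by the false share. If the false events were in truth exacerbations, the pull would be towards the exacerbation HR rather than towards 1.

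**The case against.** **Diagnosis position.** A reader might infer that the outcome accepts its codes in any position, so that pneumonia arising during any stay is counted. The text does not say so; it is silent. Section 8.4.2.1 also restates its principal-diagnosis event as a hospitalisation for COPD, so the parallel phrase for pneumonia could mean principal diagnosis. This stands, and it limits the finding to an unstated position. It does not remove the conflict between the lists or the non-specific codes, which count as a principal diagnosis as well.

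**Precedent.** The body list is defended by use in two earlier COPD studies, and comparability is a fair aim. But prior use gives no predictive value here and does not explain why the annex differs. A sensitivity analysis keeps the comparability.

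**Annex status.** The annex is provisional and omits all five non-specific body codes, so the final list might be sound. That would still leave the annex-only codes and the ICD-9/ICD-10 mismatch to settle.

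**Calendar time.** Calendar year of entry is a listed covariate (section 8.4.4), which limits any difference between groups due to the coding change. It does not make the outcome the same event before and after. Nor can one say that the definition simply narrows in October 2015: J12 without 480, or J69.0 without 507, widens it, while 514 without an evident counterpart narrows the body list.

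**Stakes.** Pneumonia might be taken for the study's only safety outcome. That cannot be confirmed, because the text available here has nothing between sections 8.4.2.2 and 8.4.4, and lacks section 8.9.2, to which section 8.4.1 refers for sensitivity analyses. Nor does anything in the documents show that the false share is as high as 20% to 30%; at 5% to 10% the shift is small.

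**Conclusion.** The concern holds as a defect of specification. The protocol carries two pneumonia lists that disagree in both directions, neither fits the community-acquired label, neither is matched across the coding change, and no diagnosis position is given. Non-pneumonia or hospital-onset stays can count; the documents do not show that they will, or how often.

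The likely direction is towards the null, by the protocol's own reasoning. Over an assumed false share of 5% to 30%, a true HR of 0.70 reads 0.715 to 0.79. This rests on three assumptions: the share itself, equal rates of false events in both groups, and standard ICD labels for the disputed codes. The composite adverse outcome inherits the problem, mixed with its other components. The primary outcome is untouched. The point should be settled before analysis, but it does not threaten the main result.

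**What to change.** - State one governing list in section 8.4.2.2 and make Annex 3.2 identical to it.
- Match ICD-9 and ICD-10 codes, for example 480 with J12, 487.0 with J10.0 and J11.0, and 507 with J69. Record a keep-or-drop decision for the other codes on which the lists differ (510.0, 510.9, 513.0, 517.1, J85.0, J86).
- Drop 511.0, 514, 519.8, 530.84, J22, 997.31, 997.32, J95.4 and J95.89.
- Require the pneumonia code as the principal discharge diagnosis, as for severe exacerbation. This also serves as the working rule for community onset, and the text should say so.
- Apply the same definition in the composite outcome.
- Keep the present section 8.4.2.2 list, in any position, as a sensitivity analysis for comparison with the cited studies.

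The cost is protocol wording and a re-run on existing claims. Some true pneumonias coded in a secondary position will be lost; comparison with the sensitivity analysis will show how far this matters.
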